5.3.3 Removal of Subjects from the Study

Subjects may withdraw or be withdrawn from the study for the following reasons:

1. At their own request or at the request of their legally acceptable representative.
2. If, in the investigator’s opinion, continuation in the study would be detrimental to the subject’s well-being.
3. At the specific request of the sponsor.*
 - * Subjects will only be removed at the request of the sponsor if a safety concern is identified that may potentially cause harm to a subject or if the risk of the specified treatment outweighs the benefit.
4. Post-consent decision due to inclusion error (determination of ineligibility based on safety or eligibility criteria).
5. Physician’s judgment following an adverse event (AE) post-treatment.
6. Termination of the trial by a regulatory authority.

In all cases, the reason for withdrawal must be recorded in the electronic case report form (eCRF) and in the subject’s records.

5.3.4 Subject Replacement

Subjects who are randomized and withdrawn from the study will not be replaced.

5.3.5 Follow-up of Subjects Withdrawn from Study

If possible, blood samples will be obtained to complete the pertinent tests at the time of subject withdrawal. In all cases, the reason for withdrawal must be recorded in the eCRF and in the subject’s records. No subject can be re-enrolled into the study after having been withdrawn from the study.

Subjects who receive any amount of IP and discontinue early from the study should have all Day 90 procedures performed at the time of withdrawal (preferably within 1 week of withdrawal).

GRIFOLS Bioscience Industrial Group	Number IG1407 - Effects of Plasma Exchange with Human Serum Albumin 5% (PE-A 5%) on Short-term Survival in Subjects with "Acute-On-Chronic Liver Failure" (ACLF) at High Risk of Hospital Mortality	BIG-CL-PRT-000002	Version 6.0	Status	Retired	Effective Date	29-Mar-2023
						Page	50 of 102

All efforts should be made to collect the vital status of the subject (including data on liver transplantation, subject survival, and cause of death) at Hospital Discharge, Day 28, and Day 90.

6 TREATMENT OF SUBJECTS

6.1 Administration and Timing of Investigational Product for Each Subject

6.1.1 PE-A 5% Dosage, Procedures, and Treatment Regimen

See [Section 4.4](#) for the treatments to be administered, including the name of the product, the dose, the dosing schedule, and the route/mode of administration.

6.1.1.1 Plasma Exchange Procedures

Plasma exchange treatment (PE-A 5%) will be performed using 5% albumin solution (Albutein 5%). Fresh frozen plasma will be administered after the 5% albumin administration to prevent coagulopathy, and the PE-A 5% session is considered completed at the end of the FFP administration. In subjects without severe coagulopathy ($\text{INR} \leq 3$), two-thirds of the volume exchanged will be replaced with albumin 5% and one-third with FFP. In subjects with severe coagulopathy ($\text{INR} > 3$), half of the volume exchanged will be replaced with albumin and half with FFP.

One-point-two (1.2) plasma volumes will be exchanged per PE-A 5% session. Total blood volume will be calculated according to Nadler's formula ([Appendix 3](#)). Plasma volume will be estimated from the calculated TBV and the HCT. The volume to be exchanged will be considered as the volume to be infused (not the fluid to be removed).

The formula for calculating plasma volume to obtain the total volume to be exchanged is as follows:

$\text{Plasma volume} = \text{TBV} \times (1 - \text{HCT})$ $\text{Total volume to be exchanged} = \text{Plasma volume} \times 1.2$

Note: plasma volume is in mL; HCT = hematocrit, TBV = total blood volume in mL

Plasma exchange will be performed using centrifugation or plasma filtration techniques ([44,46](#)). Citrate or heparin will be used as anticoagulant therapy. Vital signs of each subject and coagulation parameters will be controlled during each PE-A 5% session.

6.1.1.2 Treatment of Potential Complications Related to Plasma Exchange

Cardiovascular monitoring, Cardiac Overload Treatment, Coagulation Disturbances, and IVIGs Side Effects

GRIFOLS
 
Bioscience Industrial Group
	Number	BIG-CL-PRT-000002 IG1407 - Effects of Plasma Exchange with Human Serum Albumin 5% (PE-A 5%) on Short-term Survival in Subjects with "Acute-On-Chronic Liver Failure" (ACLF) at High Risk of Hospital Mortality	Version	6.0	Status	Retired	Effective Date	29-Mar-2023
							Page	51 of 102

Evaluation of cardiovascular function will be performed by continuous monitoring of vital signs during hospital admission (mean, systolic and diastolic arterial pressure, HR, and SpO₂). These vital parameters will be strictly monitored before, during, and after each PE-A 5% session. Arterial pressure will be measured non-invasively in subjects with hemodynamic stability and invasively, through an arterial line, in any subject experiencing shock during the procedure. Central venous pressure will be periodically monitored in all subjects through a central line catheter. Estimation of cardiac function will be mandatory in subjects with shock and can be performed by different techniques according to local guidelines (echocardiography, pulse wave analysis, Pulse index Contour Continuous Cardiac Output, Lithium Dilution Cardiac Output, Swan-Ganz).

Plasma Exchange is an euvolemic procedure. Therefore, cardiac overload/pulmonary edema is an unexpected side effect in subjects receiving PE-A 5%. In subjects with the diagnosis of cardiac overload (unrelated side effect), standard protocols will be applied as per institution standards and may include fluid restriction, IV administration of furosemide, and Renal Replacement Therapy (RRT) if clinically indicated (diuresis lower that 0.5 mL/kg under high doses of furosemide). See [Appendix 8](#) for an example of Algorithm for Cardiogenic Pulmonary Overload.

In the case of clinically relevant alterations in the coagulation parameters after PE (fibrinogen <1 g/L, platelet <20,000/μL), transfusion (fibrinogen or platelets) will be carried out in order to prevent bleeding complications related to the procedure.

If an AE occurs during the infusion of IVIGs, the rate of the infusion should be reduced or the infusion should be stopped depending on the nature and severity of the event until all symptoms disappear. After re-evaluation of the AE, the infusion may be restarted and increased to a tolerated rate. If a subject experiences a second AE, the infusion should be stopped immediately.

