8 ASSESSMENT OF SAFETY

8.1 Safety Variables

- The number of suspected ADRs, including adverse reactions (ARs), and incidence rate of subjects with suspected ADRs during the treatment period and within 72 hours after PE-A 5% completion (or after PE-A 5% stops) will be considered as the main safety variables. The number and incidence rate of overall AEs and SAEs, as well as deaths and discontinuations due to AEs will be also collected and analyzed.
- Vital signs will be recorded at each scheduled visit and in particular before and after each PE-A 5% session.
- Clinical laboratory test parameters (blood cell counts, platelet count, INR, fibrinogen, etc.) will also be assessed according to the study schedule.
- Physical examinations will be assessed according to the study schedule.
- According to the investigator's assessment, all clinically relevant changes in vital function and laboratory testing parameters findings will be considered AEs.

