8.3.4 Assessment of Causality of Adverse Event

The investigator is required to provide a causality assessment for each AE reported to the Sponsor. The Sponsor will consider the investigator’s causality assessment and also provide its own assessment. Causal relationship to the study drug will be established according to medical judgment on whether there is a **reasonable possibility of a causal relationship between the AE and the study drug**.

The investigator must determine and classify the AE causality according to the following categories:

Unrelated/Not related: there is not a reasonable possibility of causal relationship between the AE and the study drug.

Possibly related: there is evidence to suggest a causal relationship between the study drug and the AE.

Definitely related: there is a reason to conclude that the study drug caused the AE.

Criteria to assess the causal relationship should take into account of the following conditions:

- A plausible temporal sequence from the study drug administration to the AE onset
- Whether the event follows a known response pattern to the suspected treatment
- Whether the AE could be reasonably explained by the subject’s clinical state, comorbidities, or concomitant medications
- The occurrence of improvement on stopping/reducing the treatment (positive dechallenge) and/or reappearance of the event on repeated exposure (positive rechallenge)

For expedited safety reporting purposes, AEs assessed as either “definitely related” or “possibly related” will be considered POTENTIALLY RELATED or just RELATED.

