9.1.3.1 Adverse Events

Adverse events will be coded and classified using MedDRA® terms (system organ class and preferred terms).

When a causal relationship of an AE is classified by the investigator as definitely or possibly related, the event will be defined as a suspected ADR. A suspected ADR with a causal relationship of “definitely related” will be defined as an AR. The sponsor will consider the investigator’s causality assessment and also provide its own assessment. If there is any disagreement in causality assessment between the investigator and the sponsor, a separate summary of suspected ADRs/ARs will be provided.

For summary purpose, AEs will be classified as treatment-emergent AEs (TEAEs) or non-TEAEs depending on the comparison of AE onset date/time with the start date/time of study treatment. A TEAE will be defined as an AE which occurs between the start of study treatment and the final visit of the clinical study. A non-TEAE will be defined as an AE which occurs prior to the start of study treatment. Non-TEAEs and TEAEs will be summarized separately.

In addition, TEAEs, including suspected ADRs, will be summarized by each treatment group, system organ class, preferred term, causal-relationship, severity, and seriousness (serious versus non-serious) using descriptive statistics. At each level of summarization, a

subject will only be counted once per system organ class or preferred term using the most severe AE or the AE with the strongest causal relationship to the treatment.

AEs (including suspected ADRs) temporally associated with PE-A 5% (ie, those occurring during a PE session or within 72 hours after the completion of a PE session) will be summarized by presenting incidences and percentages and listed.

Subjects with SAEs, AEs leading to death, or who withdraw from the study because of an AE will also be individually listed and summarized.

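### Protocol 6.1.1.2 calls cardiac overload unrelated in advance, against the case-by-case causality rule in 8.3.4, so suspected ADRs may under-count it

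*Protocol*

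**What the plan says.** Protocol 6.1.1.2, headed as dealing with complications related to plasma exchange, argues that the procedure is euvolemic and that cardiac overload or pulmonary edema is therefore unexpected. It continues: "In subjects with the diagnosis of cardiac overload (unrelated side effect), standard protocols will be applied as per institution standards".

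Protocol 8.3.4 sets the causality procedure: "The investigator is required to provide a causality assessment for each AE reported to the Sponsor". The first criterion it lists is "A plausible temporal sequence from the study drug administration to the AE onset". The others are a known response pattern, alternative explanations, and dechallenge or rechallenge. The sponsor adds its own assessment.

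Protocol 8.1 makes the count of suspected ADRs and the "incidence rate of subjects with suspected ADRs during the treatment period and within 72 hours after PE-A 5% completion" the main safety variables. Protocol 9.1.3.1 supplies the definition: an AE "classified by the investigator as definitely or possibly related, the event will be defined as a suspected ADR". SAP 10.1 keeps that definition. Protocol 9.1.3.1 also promises a separate ADR/AR summary where sponsor and investigator disagree.

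Protocol 8.3.3.1 and 8.3.10 treat sequelae of ACLF, including failure of the circulation or lung, as disease progression rather than AEs unless there is evidence of a causal link to the study drug. Such events are documented in the eCRF and medical record but are not immediately reported to the sponsor.

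**The concern.** A site that consults 6.1.1.2 when a patient develops pulmonary edema after an exchange finds the relatedness question already answered. A site that consults 8.3.4 is told to work it out from the timing and the clinical picture. The two sections give different guidance on the one field that decides whether the event counts as a suspected ADR.

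The trial is open-label and the label concerns recipients of PE-A 5%, so any resulting bias runs one way: toward under-counting a plausible harm of the procedure. The same label also bears on the prior question of whether the event is an AE at all, because the disease-progression exception turns on evidence of causality.

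**Working it through.** There is no sample size, power or alpha figure to reproduce. The check compares sections and tests one quantity by arithmetic.

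**1. Does the label conflict with the causality rule?** Section 6.1.1.2 gives a generic reason (exchange is euvolemic) and a fixed answer (unrelated). Section 8.3.4 demands a judgement for each event on stated criteria and makes no exception for overload. Both cannot guide the same rating, so the conflict is on the page.

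**2. Does it reach the main safety variable?** Overload is recorded as an AE → the investigator chooses not related, possibly related or definitely related → only the last two make a suspected ADR (Protocol 9.1.3.1, SAP 10.1). The label acts on the middle step. It can bias the choice; it does not make it.

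**3. What happens to an event rated not related?**

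| Output or route | Depends on the investigator's causality rating? | Still captures the event? |
|---|---|---|
| Suspected ADR and AR tables (SAP 10.1) | Yes | No |
| Sponsor's own assessment (8.3.4) and disagreement summary (9.1.3.1) | No | Yes, but SAP 10.1 lists no such summary |
| SAE to sponsor within 24 hours (8.3.11.1), evaluated for expedited reporting (8.3.7) | No | Yes, if serious |
| TEAE and serious-TEAE tables (SAP 10.1) | No | Yes (serious table only if serious) |
| AEs during a session or within 72 hours after it (9.1.3.1, SAP 10.1) | No | Yes, if in the window |
| Classification for onward expedited reporting (8.3.4, 8.3.6) | Relatedness matters, but the sponsor also assesses it | Possibly |

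The routes that capture the event presuppose that it was recorded as an AE.

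**4. Is that recording secure?** Overload that presents as respiratory or circulatory failure falls within the organ failures named in 8.3.3.1 and 8.3.10. It stays an AE only if evidence suggests causality, and 6.1.1.2 has just said there is none. If it is treated as progression, SAP 10.2 and 9.3.8 may still show an organ failure, but neither identifies overload. Overload is not named in the non-exhaustive list of expected AEs in 8.3.1, and 8.3.9 names no events of special interest.

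**5. Does the volume exchanged show net overload?** The inputs are 1.2 plasma volumes (6.1.1.1) and Nadler's formula (Appendix 3). Body size and hematocrit (HCT) are assumed.

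- Volume per session = 1.2 × TBV × (1 − HCT).
- Man, 1.75 m, 80 kg, HCT 0.30: TBV = 0.3669 × 1.75³ + 0.03219 × 80 + 0.6041 = 5.15 L. Volume = 1.2 × 5.15 × 0.70 = 4.3 L, or 17.3 L over 4 sessions and 38.9 L over 9.
- Assumed range: 2.3 L (woman, 1.55 m, 50 kg, HCT 0.40) to 5.8 L (man, 1.85 m, 110 kg, HCT 0.25) per session.

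These are gross infused volumes. Section 6.1.1.1 defines the target by what is infused, 8.3.1 states that the same amount is extracted, and 2.3 says removal and replacement are simultaneous. SAP 8.3 and 8.4 plan no summary of removed volume or fluid balance. The IVIG concentration is not given, so its volume cannot be added. Net gain is not derivable.

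**The case against.** The strongest reply is that the parenthesis sits in a paragraph about managing a complication and is not a coding instruction. Section 8.3.4 governs causality, exempts nothing and adds sponsor review. Serious events reach the sponsor whatever their rating. The causality-free tables and the 72-hour summary would show a recorded event, including one two hours after a session. SAP 5.4.2 lists overall AEs and SAEs under main safety variables, so the SAP's safety picture does not rest on ADRs alone. Patient visits have ended, so editing the protocol cannot change a rating.

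All of this stands, and it limits the consequence to a risk of under-counting. A reader might infer more: that overload is absent from every ADR and AR table by instruction, that it escapes expedited reporting, or that litres exchanged demonstrate overload. The documents do not support these readings. The investigator must still rate each event, the sponsor evaluates every serious event, and the volumes are gross. Section 6.1.1.2's own word *unexpected* does not settle expectedness either, since 8.3.6 leaves that to the sponsor and the reference document.

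The reply does not remove the contradiction, and it relies on safeguards with two gaps: the event must first be recorded as an AE, and the promised disagreement summary is missing from SAP 10.1.

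**Conclusion.** The concern holds as a contradiction between 6.1.1.2 and 8.3.4 that can bias investigator ratings toward not related. Overload is therefore at risk of being under-counted among suspected ADRs and, through the disease-progression rule, of not being recorded as an AE. That some sites were influenced by the label is an assumption; the documents neither show nor exclude it. The size cannot be given: no overload rate, removed volume or rating data are in the documents. The direction is clear, toward fewer suspected ADRs on PE-A 5%. The primary and secondary efficacy analyses are unaffected.

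**What to change.** **Protocol.** Reconcile 6.1.1.2 with 8.3.4, 8.3.10 and 8.3.11.1: delete the parenthetical label and state that cardiac overload or pulmonary edema is recorded as an AE and rated under 8.3.4. No change to clinical management is proposed.

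**SAP 10.1.** Add one by-arm row for fluid overload or pulmonary edema irrespective of causality, from the MedDRA terms already coded, and include any such events captured on the disease-related complications page (SAP 10.2). Existing tables already show the coded terms; the row gathers them in one place and picks up events filed as progression. Fix the term list in writing before counting by arm. Add the sponsor-investigator disagreement summary promised in Protocol 9.1.3.1.

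**Clinical study report.** SAP 2 gives April 14, 2025 as the last patient visit, and SAP 3.0 is dated October 15, 2025, so a site memo cannot alter ratings already made. Disclose the advance label as a limitation of the ADR counts.

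The cost is a few deleted words and a sentence in the protocol, one table row, one summary already promised, and a short paragraph in the report.

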6.1.1.3 PE-A 5% Treatment Regimen

A minimum of 4 and a maximum of 9 PE-A 5% sessions will be performed in each subject. The number of PE-A 5% sessions will be determined by the pattern of response (complete response, no response, or partial response) to PE-A 5% treatment ([Table 6-1](#) and [Table 6-2](#)) and is described briefly below:

Treatment schedule consists of 2 initial PE-A 5% sessions on consecutive days followed by every other day PE-A 5% sessions. The aim of the study is to achieve complete response (resolution of ACLF or improvement to ACLF-1a):

- Subjects with very early complete response after 1 or 2 PE-A 5% sessions (resolution of ACLF or improvement to ACLF-1a) will receive 3 or 2 additional PE-A 5% sessions, respectively, to consolidate the response because the total number of PE-A 5% sessions should not be lower than 4. See [Table 6-1](#) for details.
- Subjects with very early complete response after 3 PE-A 5% sessions (resolution of ACLF or improvement to ACLF-1a) will receive 2 additional PE-A 5% sessions to consolidate the response.

- Subjects with complete response after 4 PE-A 5% sessions (resolution of ACLF or improvement to ACLF-1a) will receive 2 additional PE-A 5% sessions to consolidate the response. See [Table 6-1](#) for details.
- Subjects with no response (subject with no change or worsening of ACLF grade) after 4 PE-A 5% sessions will discontinue treatment so the total number of PE-A 5% sessions will be 4.

Table 6-1 PE Schedule (Number of Sessions) according to the Clinical Response to Treatment (Complete and No Clinical Responses)

Very early complete clinical response after the first 1 or 2 PE sessions ^a											
PE	▲ #1	▲ #2	■	▲ #3		▲ #4	■				
Day	1	2	3	4	5	6	7				
Very early complete clinical response after the first 3 PE sessions ^b											
PE	▲ #1	▲ #2	■	▲ #3		▲ #4	■	▲ #5	●		
Day	1	2	3	4	5	6	7	8	9		
Complete clinical response after the first 4 PE sessions ^c											
PE	▲ #1	▲ #2	■	▲ #3		▲ #4	■	▲ #5		▲ #6	■
Day	1	2	3	4	5	6	7	8	9	10	11
No clinical response after the first 4 PE sessions ^d											
PE	▲ #1	▲ #2	■	▲ #3		▲ #4	■				
Day	1	2	3	4	5	6	7				

- ^a These subjects will receive 3 or 2 additional PE-A 5% sessions following complete clinical response and therefore will receive a total of 4 PE-A 5% sessions.
- ^b These subjects will receive 2 additional PE-A 5% sessions following complete clinical response and therefore will receive 5 PE-A 5% sessions.
- ^c These subjects will receive 2 additional PE-A 5% sessions following complete clinical response and therefore will receive 6 PE-A 5% sessions.
- ^d These subjects with no response after 4 PE-A 5% sessions will discontinue the treatment so the total number of PE-A 5% sessions will be 4.

▲ PE = PE-A 5% session, ■ IGIV = 200 mg/kg every 2 PE sessions, ● IGIV = 100 mg/kg 1 day after the last, odd-numbered PE session

- Subjects with partial response after the first 4 PE-A 5% sessions (reduction of 1 organ failure or more to ACLF-1b or ACLF-2) will be treated accordingly: as described below:
 - Subjects with partial response who in the course of the additional PE-A 5% sessions show complete response will receive 2 consolidating sessions after achieving complete response. See [Table 6-2](#) for details.
 - Subjects with partial response who in the course of the additional PE-A 5% sessions worsen to ACLF-3b will be discontinued for the PE-A 5% sessions.
- In summary, regardless of the type of response, the total number of sessions should never be lower than 4 or higher than 9.

Table 6-2 PE Schedule (Number of Sessions) according to the Clinical Response to Treatment (Partial Clinical Responses after the First 4 PE Sessions)

Achieve complete response at 5 th PE session ^a												
PE	▲ #1	▲ #2	■	▲ #3		▲ #4	■	▲ #5		▲ #6	■	▲ #7
Day	1	2	3	4	5	6	7	8	9	10	11	12
PE	●											
Day	13											
Achieve complete response at 6 th PE session ^b												
PE	▲ #1	▲ #2	■	▲ #3		▲ #4	■	▲ #5		▲ #6	■	▲ #7
Day	1	2	3	4	5	6	7	8	9	10	11	12
PE		▲ #8	■									
Day	13	14	15									
Achieve or do not achieve complete response after 7 th PE session ^c												
PE	▲ #1	▲ #2	■	▲ #3		▲ #4	■	▲ #5		▲ #6	■	▲ #7
Day	1	2	3	4	5	6	7	8	9	10	11	12
PE		▲ #8	■	▲ #9	●							
Day	13	14	15	16	17							

^a These subjects will receive 2 additional PE-A 5% sessions following complete clinical response at the 5th PE-A 5% session and therefore will receive a total of 7 PE sessions.

^b These subjects will receive 2 additional PE-A 5% sessions following complete clinical response at the 6th PE-A 5% session and therefore will receive a total of 8 PE-A 5% sessions.

^c Regardless of the response after the 7th or 8th session, subjects will receive the remaining 2 or 1 PE-A 5% sessions so the total number of PE-A 5% sessions will be 9.

▲ PE = PE-A 5% session, ■ IGIV = 200 mg/kg every 2 PE sessions, ● IGIV = 100 mg/kg 1 day after the last, odd-numbered PE session

IVIGs will be administered intravenously at a dose of 200 mg/kg 1 day after every 2 PE-A 5% sessions in order to prevent the development of hypogammaglobulinemia and infection. In those subjects receiving an odd number of PE-A 5% sessions (eg, #5, #7, or #9 PE-A 5% sessions when they are the last PE session for the subject), IVIGs will be administered 1 day after this PE-A 5% session at a dose of 100 mg/kg. Initial infusion rate of IVIGs will be of 0.5 mL/kg/hour, increasing to a maximum rate of 2 mL/kg/hour if tolerance is adequate.

The entire follow-up period will be 90 days after randomization. Detailed procedures can be found in [Figure 4-1](#), [Section 7.2.1](#), [Appendix 1](#), and [Appendix 2](#).

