- The inclusion in the study of subjects with ACLF-1b, ACLF-2 or ACLF-3a at the time of diagnosis, excluding subjects with ACLF-1a and ACLF-3b, would reduce heterogeneity from a 90-day mortality rate ranging between 25 to 90% and 42 to 66% without a major reduction in the study population (only 25%).
- ACLF-1a resolves with SMT in a high proportion of subjects. Moreover, these subjects show relatively low 90-day mortality (25%) and may reach liver transplantation on a standard wait list. Treating ACLF-1a with PE-A 5% seems, therefore, unnecessary.
- In contrast, 90-day mortality rate in subjects with ACLF-3b is extremely high (90%) making them poor candidates for an invasive procedure such as proposed in the current trial.

Table 2-2 28-Day and 90-day Mortality Rates in Patients with Different Grades of ACLF at Diagnosis and 3-4 Days Later (CANONIC Study)

	28-day mortality		90-day mortality	
	At diagnosis	3-4 days after diagnosis	At diagnosis	3-4 days after diagnosis
NO ACLF				
Prevalence	-	23%	-	-
Mortality	-	10%	-	18%
ACLF-1a				
Prevalence	20%	10%	-	-
Mortality	15%	13%	25%	27%
ACLF-1b				
Prevalence	30%	18%	-	-
Mortality	31%	16%	42%	31%
ACLF-2				
Prevalence	36%	23%	-	-
Mortality	30%	37%	44%	52%
ACLF-3a				
Prevalence	9%	18%	-	-
Mortality	60%	58%	66%	65%
ACLF-3b				
Prevalence	5%	8%	-	-
Mortality	90%	91%	90%	97%
ACLF-1b/2/3a				
Prevalence	74.5%	58%	-	-
Mortality	34%	37%	46%	50%

Source: (13)

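### After session 7 or 8, Protocol 6.1.1.3 tells sites both to stop and to continue PE-A 5% in a partial responder who worsens to ACLF-3b

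*Protocol*

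**What the plan says.** Protocol Section 6.1.1.3 makes the number of PE-A 5% sessions depend on response and refers to Tables 6-1 and 6-2 for the schedules. A partial response is a loss of at least one organ failure that brings the subject to ACLF-1b or ACLF-2. Three statements govern what happens to a subject with a partial response after session 4.

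- The bullet: "Subjects with partial response who in the course of the additional PE-A 5% sessions worsen to ACLF-3b will be discontinued for the PE-A 5% sessions". It names no session number.
- Table 6-2, whose title limits it to "Partial Clinical Responses after the First 4 PE Sessions". Its third row is headed "Achieve or do not achieve complete response after 7 th PE session". Footnote c to that row says: "Regardless of the response after the 7th or 8th session, subjects will receive the remaining 2 or 1 PE-A 5% sessions" and gives the result as "so the total number of PE-A 5% sessions will be 9".
- The closing summary: "regardless of the type of response, the total number of sessions should never be lower than 4 or higher than 9".

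SAP Section 5.3.1 repeats the bullet and the summary, and SAP Table 5-2 (Section 5.1) repeats the row and footnote c. Neither document says which statement prevails.

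Two SAP sections depend on the schedule. Section 8.3 counts subjects who missed a PE-A 5% treatment scheduled by the protocol. Section 8.4 computes PE compliance as actual over expected exchanges.

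**The concern.** The bullet and the footnote address the same people. A partial responder who worsens to ACLF-3b after session 7 or 8 meets the condition in the bullet. The same subject has not achieved complete response and so also belongs to the third row of Table 6-2. One text says stop, the other says finish the course, and whatever the site does departs from one of them.

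The question is whether an invasive procedure goes on in a subject with four or more organ failures. Section 2.6 says of this grade: "90-day mortality rate in subjects with ACLF-3b is extremely high (90%) making them poor candidates for an invasive procedure". That sentence explains why such patients are not enrolled and is not a stopping rule on treatment, but it shows why the instruction should be unambiguous.

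No other rule clearly settles the case. The events listed in Section 5.3.2 for stopping study treatment do not name worsening of the ACLF grade. Section 8.3.10 treats new organ failure as disease progression rather than an adverse event unless a causal link is suspected. Section 5.3.3 allows withdrawal on the investigator's opinion, but that is withdrawal from the study.

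For the analysis, a scheduled session cannot be called missed, or a stop called a deviation, until the schedule for this subject is defined.

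**Working it through.** No sample-size or power formula applies. The check applies both rules to the same subject and follows the result into the SAP.

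**Inputs.** Sessions fall on two consecutive days and then every other day (Protocol 6.1.1.3). Bullet and footnote c are as quoted. Duration of exposure is the last PE-A 5% date minus the first, plus 1 (SAP 8.3). Expected exchanges are duration/2 + 1, rounded down, and set to 9 if there are more than 16 days on treatment (SAP 8.4).

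**Step 1: reproduce the schedule.** Sessions 1 to 9 fall on Days 1, 2, 4, 6, 8, 10, 12, 14 and 16, as in Table 6-2. Footnote c gives 7 + 2 = 9 and 8 + 1 = 9, so its stated total of 9 is reproduced.

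**Step 2: apply both rules to a partial responder who worsens to ACLF-3b.**

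| Worsens after session | Day | Total by bullet | Total by footnote c | Sessions in dispute |
|---|---|---|---|---|
| 5 | 8 | 5 | not triggered | 0 |
| 6 | 10 | 6 | not triggered | 0 |
| 7 | 12 | 7 | 9 | 2 |
| 8 | 14 | 8 | 9 | 1 |

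The conflict begins at session 7. The summary of 4 to 9 sessions does not resolve it, because 7, 8 and 9 all lie inside that range.

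**Step 3: follow it into the SAP.**

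- SAP 8.3, missed scheduled treatments. A stop after session 7 counts as 0 missed by the bullet and 9 - 7 = 2 by the footnote. A stop after session 8 counts as 0 or 9 - 8 = 1.
- SAP 8.4, PE compliance. Stop at session 7: duration 12, expected 12/2 + 1 = 7, compliance 7/7 = 100%. Stop at session 8: duration 14, expected 14/2 + 1 = 8, compliance 8/8 = 100%.
- For comparison only, against the 9 sessions of footnote c the figures would be 7/9 = 77.8%, below the 80% cut in SAP 8.4, and 8/9 = 88.9%. The SAP does not calculate these. Its expected number follows the subject's actual duration, so its compliance figure cannot show the discrepancy.

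**The case against.** The best defence is that the two texts can be read together. Footnote c can be taken as handling the cap: two consolidating sessions no longer fit after session 8, and subjects without complete response also run to session 9. On that view its word response means complete or not complete, and the ACLF-3b bullet is a specific exception. Section 2.4.2 fits this, since it ties treatment beyond four sessions to progressive improvement. The reading is plausible, but the documents do not state it. A subject at ACLF-3b is still a subject without complete response, and Section 6.1.1.3 presents its bullets as a brief description of what the tables set out, so a site could equally let the table govern.

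A second point is that the study schema (Protocol Figure 4-1), to which the protocol also refers for the procedures, is not available in the text reviewed. It may show an exit for ACLF-3b. That cannot be assumed, and the contradiction between the written rules would remain.

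A reader might also infer that the conflict extends to sessions 1 to 3, because a subject who reaches ACLF-3b then is still carried to session 4. The documents do not support that. The bullet covers only the additional sessions after a partial response. The minimum of four is stated consistently and given a rationale in Section 2.4.2, and no response, which includes worsening, has its own row in Table 6-1 ending at four sessions. That is a design choice and no contradiction.

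**Conclusion.** The contradiction is real and narrow. It concerns subjects with a partial response after session 4 who worsen to ACLF-3b after session 7 (7 or 9 sessions) or after session 8 (8 or 9 sessions). For them the regimen cannot be followed as written, and the SAP repeats the problem. This rests on the text of the two rules and on the absence of any stated precedence.

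The documents do not say how many subjects this is. Table 2-4 might seem to size the group, but it gives 28-day final grades by initial grade in an observational cohort, does not separate ACLF-3a from ACLF-3b, and does not describe subjects who improved on plasma exchange and then worsened.

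The ITT primary analysis, power and alpha are unaffected. A reader might infer that subjects could move in or out of the per-protocol set. That is not supported: SAP 6.4.3 requires only the first 2 sessions and no major violation that might affect the primary analysis, and nothing classes stopping at 7 or 8 instead of 9 as major. What remains is the SAP 8.3 count and possibly the deviation listing in SAP 7.2.

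Nor is this a live hazard to trial participants. SAP Section 2 records early termination, with the last patient visit on April 14, 2025. It is an internal inconsistency that should be corrected, but it is not critical to the trial's conclusions.

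**What to change.** Reconcile the ACLF-3b bullet with footnote c in Protocol 6.1.1.3, and likewise in SAP 5.3.1 and SAP Table 5-2, so that a partial responder who worsens to ACLF-3b after session 7 or 8 has one instruction. Show that case explicitly in Table 6-2 and SAP Table 5-2. Which rule applies is for the sponsor's clinicians.

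In the SAP, state that missed scheduled treatments (8.3) and deviations (7.2) for these subjects are judged against the reconciled rule. Because treatment in this trial is over, the clinical study report should also say how many subjects were in this position and how many sessions each received. ACLF grade and exposure are already recorded by visit, so this needs no new data.

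The cost is wording in two documents, one added case in each table and a short listing. No patients, procedures or changes to the efficacy analyses are needed.
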